Date: July 21, 2022

Data: sent to [name] via email by PT [name]

Goal: Evaluate 7 patients with MS on functional scale prior, during, and post participation in a rehab program

Note: 7 patients is a very low sample size to have any kind of confidence in our results, especially since this is a heterogeneous group of patients with varying disease severity. These results should be considered a pilot and interpreted with caution.

Analyses:

A within subjects repeated measures ANOVA with no between subject factor was used to assess for linear and quadratic (for variables measured at all 3 time points) trends for continuous variables.

Continuous variables were: quad length, 25 foot walk test, HS length, TUG test, HIP IR ROM, HIP ER ROM. Results from these analyses are shown on page 2 (top portion of table).

Paired samples t-tests were used to assess for mean change over time for continuous variable measured at 2 timepoints (pre and post). SPSS version 28.0 was used for analyses. Results from these analyses are shown on page 2 (bottom portion of table).

The MAT and MMT measures were analyzed descriptively (no p-values). Counts and percentages are reported in table on page 3.

Summary of Statistically Significant Findings:

1. A linear trend emerged for HIP IR ROM for both the right and the left side. With ROM increasing over time.
 - a. Right side means: 6.9, 12.1, 15.3; P=.003
 - b. Left side means: 10.7, 13.4, 17.9; P=.016

Table of means over time for tests that are considered continuous measures. Variables highlighted in yellow are statistically significant. In both cases hip internal rotation increased in a significant linear fashion throughout the 3 time points.

The tests below were administered at all three time points. A repeated measures model with time as the within subjects variable and no between subjects variable was used to assess for linear and quadratic trends. There were no quadratic trends reported. There were 2 significant linear trends reported, Hip IR ROM left and right side

| Test | Mean (Std Error), pre | Mean (Std Error), during | Mean (Std Error), post | P-value |
|--------------------|-----------------------|--------------------------|------------------------|---------|
| Quad Length R | 122.5 (5.9) | 130.8 (1.6) | 130.0 (2.6) | 0.312 |
| Quad Length L | 121.7 (5.6) | 130.0 (1.3) | 130.8 (2.4) | 0.210 |
| 25 foot walk test | 21.4 (5.2) | 20.7 (5.9) | 15.0 (1.3) | 0.370 |
| Hamstring length R | 67.5 (4.4) | 52.5 (18.7) | 55.0(15.6) | 0.470 |
| Hamstring length L | 64.0 (7.8) | 72.0 (4.6) | 74.0 (3.7) | 0.189 |
| TUG Test | 27.2 (9.2) | 23.6 (6.9) | 16.5 (0.4) | 0.321 |
| Hip IR ROM R | 6.8 (1.8) | 12.1 (2.1) | 15.3 (2.1) | 0.003 |
| Hip IR ROM L | 10.7 (2.3) | 13.4 (1.3) | 17.9 (1.5) | 0.016 |
| Hip ER ROM R | 34.3 (6.3) | 38.6 (5.5) | 38.3 (6.0) | 0.199 |
| Hip ER ROM L | 35.0 (5.8) | 38.6 (5.0) | 40.0 (5.7) | 0.134 |

The data below were collected at 2 timepoints. Means from pre to post were compared using a paired samples t-test. Means \pm standard deviations are reported. P -values are not significant.

| Test | Mean \pm SD, pre | | Mean \pm SD, post | p-value |
|--------|--------------------|----|---------------------|---------|
| EDSS | 6.8 \pm 0.8 | -- | 6.8 \pm 0.8 | NA |
| MSIS29 | 97.3 \pm 25.2 | -- | 85.0 \pm 20.2 | 0.397 |
| MSWS12 | 0.89 \pm 0.14 | -- | 0.70 \pm 0.28 | 0.277 |

On the following page assessments for categorical measures are shown by the count and percentage of patients who improved, stayed the same, and worsened over time (from pre to post).

| | N worse | N same | N Improve | %worse | %same | %Improved |
|--|---------|--------|-----------|--------|--------|-----------|
| MATR hip fleX change | 0 | 5 | 2 | 0.0% | 71.4% | 28.6% |
| MATL hip flex change | 0 | 6 | 1 | 0.0% | 85.7% | 14.3% |
| MATR hip ext change | 1 | 2 | 4 | 14.3% | 28.6% | 57.1% |
| MATL hip ext change | 2 | 4 | 1 | 28.6% | 57.1% | 14.3% |
| MATR knee flex change | 1 | 4 | 2 | 14.3% | 57.1% | 28.6% |
| MATL knee flex change | 0 | 3 | 4 | 0.0% | 42.9% | 57.1% |
| MAT R knee ext change | 1 | 5 | 1 | 14.3% | 71.4% | 14.3% |
| MAT L knee ext change | 0 | 3 | 4 | 0.0% | 42.9% | 57.1% |
| MAT R ankle DF change | 1 | 6 | 0 | 14.3% | 85.7% | 0.0% |
| MAT L ankle DF change | 0 | 7 | 0 | 0.0% | 100.0% | 0.0% |
| MAT R Ankle PF change | 1 | 1 | 5 | 14.3% | 14.3% | 71.4% |
| MATL ankle PF change | 2 | 0 | 5 | 28.6% | 0.0% | 71.4% |
| MMT R psoas Change | 0 | 3 | 4 | 0.0% | 42.9% | 57.1% |
| MMT L psoas Change | 0 | 2 | 5 | 0.0% | 28.6% | 71.4% |
| MMT Rec Abd change | 0 | 3 | 3 | 0.0% | 50.0% | 50.0% |
| MMT R Quadratus Change | 0 | 2 | 5 | 0.0% | 28.6% | 71.4% |
| MMT L Quadratus Change | 0 | 3 | 4 | 0.0% | 42.9% | 57.1% |
| MMT R Rec Fem Change | 1 | 2 | 4 | 14.3% | 28.6% | 57.1% |
| MMT L Rec Fem Change | 1 | 3 | 3 | 14.3% | 42.9% | 42.9% |
| Vastus R lateralis medialis MMT Change | 1 | 1 | 5 | 14.3% | 14.3% | 71.4% |
| Vastus L lateralis medialis MMT Change | 0 | 0 | 7 | 0.0% | 0.0% | 100.0% |
| MMT R Glut Med Change | 0 | 0 | 7 | 0.0% | 0.0% | 100.0% |
| MMT L Glut med Change | 0 | 3 | 4 | 0.0% | 42.9% | 57.1% |
| MMT R Hip Add Change | 1 | 1 | 5 | 14.3% | 14.3% | 71.4% |
| MMT L Hip Add Change | 0 | 2 | 5 | 0.0% | 28.6% | 71.4% |
| MMT R Fibularii Change | 3 | 2 | 2 | 42.9% | 28.6% | 28.6% |
| MMT L Fibularii Change | 2 | 3 | 2 | 28.6% | 42.9% | 28.6% |
| MMT R Tib anterior CHANGE | 0 | 2 | 5 | 0.0% | 28.6% | 71.4% |
| MMT L Tib anterior Change | 1 | 1 | 5 | 14.3% | 14.3% | 71.4% |
| MMT R Tib posterior Change | 3 | 2 | 2 | 42.9% | 28.6% | 28.6% |
| MMT L Tib posterior Change | 2 | 3 | 2 | 28.6% | 42.9% | 28.6% |
| MMT R toe Ext Change | 1 | 2 | 4 | 14.3% | 28.6% | 57.1% |
| MMT L toe Ext Change | 2 | 3 | 2 | 28.6% | 42.9% | 28.6% |
| MMT R toe flex Change | 2 | 2 | 3 | 28.6% | 28.6% | 42.9% |
| MMT L toe flex Change | 1 | 4 | 2 | 14.3% | 57.1% | 28.6% |
| MMT lumbar ext B | 1 | 0 | 4 | 20.0% | 0.0% | 80.0% |
| MMT R glut max Change | 0 | 3 | 4 | 0.0% | 42.9% | 57.1% |
| MMT L glut max Change | 2 | 2 | 3 | 28.6% | 28.6% | 42.9% |
| MMT R biceps Fem Change | 0 | 2 | 4 | 0.0% | 33.3% | 66.7% |
| MMT L biceps Fem Change | 0 | 1 | 5 | 0.0% | 16.7% | 83.3% |
| MMT R semitendinosis semimembranosis | 0 | 2 | 5 | 0.0% | 28.6% | 71.4% |
| MMT L semitendinosis semimembranosis | 1 | 4 | 2 | 14.3% | 57.1% | 28.6% |

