The study will require up to 10 weeks of various form of appointments, testing and active therapy participation. Specifically, you will need an initial appointment with [name] to understand and sign our consent form as well as initial testing in EDSS, then you will be arranged in same office on same day to see [name] for H-reflex testing. Once these steps are complete, you will be referred by [name] to Centura Health at Home to work with [name] for visits 3 times per week over a period of 6 weeks. She will come directly to your home for all portions of treatment and assessments. [name] will perform testing and treatment using an FDA approved direct current electrical stimulation device and exercise, stretches and a form of manual therapy known as primary and secondary activations. Once the treatment portion of the study is complete you will need to have a follow-up appointment with [name] and [name] for re-testing.

1. If you would like to consult further prior to making a decision please contact the primary investigator directly:
 - a. [name], PT, DPT
[contact]
[contact]
2. If you are certain you would like to be a participant, please call Colorado Neurodiagnostics directly to arrange an initial appointment with [name]. Please mention your interest in the Pilot study participation when calling.
 - a. Colorado Neurodiagnostics (coneurodiagnostics.com)
 - i. [contact]

Thank you for your time and consideration.

Sincerely,

[name], PT, DPT

Study Timelines

- All participants will be referred through [name]. We will plan to start with only one participant for the first case study to ensure all steps completed as planned. Then the second case study is to begin as soon as the first one is completed and on until up to 9 case studies are completed. [name] will start with one participant at a time, then once all steps completed will be open to treating to 2 study subjects at a time.
- Depending on timeline for IRB approval and Centura approval we hope to begin this study in the Spring of 2021 and depending on

number of subjects and timeliness of finishing one case study and starting the next we'd hope to complete the study by Winter of 2021.

Study Endpoints

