The primary study endpoint of this pilot study to assess if decrease in spasticity for individuals with MS is possible during NeuBie direct current treatment and for any length of time after treatment to further learn if this correlates to improvement in functional gait and transfers. The listed subjective and objective data points are selected to capture this endpoint.

Procedures Involved

Study methods:

1. Treatment portion of study:
2. The physical therapist will implement manual activation techniques combined with NeuBie and PT exercise interventions 3 times per week for 6 weeks.
 - i) Use of Treatment table with manual activations to underactive, spastic or limited in sensory muscles/regions (The PT will consider primary and secondary activations to strengthen neural pathways maximally)
 - ii) NeuBie Mapping mode scanning process with electrode placed on thoracolumbar space and second sponge electrode scanning for:
 - (1) Spots that stimulate movement they couldn't do before per initial assessment
 - (2) Spots that allow movement which is a greater range than available before per initial assessment
 - (3) Spots that lead to decreased spasticity (turn up amplitude and have participant work through the threat response then repeat)
 - (4) Diminished sensation areas – drive signal to increase sensory nerves and become metabolically active. Consider knee, hip and ankle joints as these are neurologically rich.
 - iii) Train using physical therapy exercises with Neubie in training mode and Hz current adjusted for tolerance, ability to work through or decrease spasticity in (500 Hz) in the following areas (spasticity, contraction, dead or diminished spots and hot spots) as tolerated but remove if participant is displaying signs of fatigue
 - (1) Spasticity areas – 500Hz – adjust amplitude to 7/10 discomfort and Pt works through spasticity with assist from PT as needed. The muscle that oppose the spasticity (agonist) will be considered for 40Hz current adjusted no higher than 7/10 discomfort with movement patterns out of the spasticity.
 - (2) Contraction areas -500Hz – adjust amplitude to 7/10 intensity and participant works with contracting muscle without altered kinematics or co-contraction. The muscle that oppose the spasticity (agonist) will be considered for 40Hz current adjusted no higher than 7/10 discomfort with movement patterns out of the spasticity.

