- (3) Dead/diminished areas – establish a baseline amplitude for sensation and leave signal on at this amplitude. Over time assess if the amplitude for sensation is decreased demo return of sensation.
- (4) Hot spots – assess if the same amplitude over these areas which creates high level of discomfort becomes less uncomfortable over time as a sign of increased neurological resiliency.
- iv) Continue with electrodes in place and apply with functional training in high kneeling, sitting, transfers, standing static, standing dynamic closed chain, standing dynamic open chain, gait and movements available in LE/core
- v) Progress participant in sitting balance unsupported, sit to stand, standing balance static and dynamic and in gait
- vi) If participant tolerates less amplitude signal next visit while working through spasticity or contraction, they are in neurological fatigue and consider master re-set, sensory inputs, stretches and more gentle approach for active recovery

If participant was not receiving this intervention, they would receive traditional physical therapy in stretching, therapeutic exercise training open chain and closed chain, transfer training, gait training and balance training working within limits of participant's spasticity levels.

Participants in this study will participate in the listed interventions for 6 weeks. Outcome measures objective and subjective will be collected at the beginning and end of the study.

1. EDSS – [name] performs (<https://www.mstrust.org.uk/a-z/expanded-disability-status-scale-edss>)
2. Hoffman's Reflex – [name] performs ([name] performs test only, then gives results to investigators.) (<https://www.ncbi.nlm.nih.gov/pmc/articles/PMC522151/>)
3. 12 item MS walking scale –[name] performs <https://www.sralab.org/sites/default/files/2017-07/msws-eng.pdf>
4. Manual Muscle test – [name] performs
5. Modified Ashworth test – [name] performs <https://www.sralab.org/sites/default/files/2017-06/Modified%20Ashworth%20Scale%20Instructions.pdf>
6. 25 foot walk test – [name] performs [https://www.nationalmssociety.org/For-Professionals/Researchers/Resources-for-Researchers/Clinical-Study-Measures/Timed-25-Foot-Walk-\(T25-FW\)](https://www.nationalmssociety.org/For-Professionals/Researchers/Resources-for-Researchers/Clinical-Study-Measures/Timed-25-Foot-Walk-(T25-FW))
7. Timed up and Go –[name] performs https://www.cdc.gov/steadi/pdf/TUG_test-print.pdf

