8. Multiple Sclerosis Impact Scale (MSIS-29) – [name] performs <https://www.mstrust.org.uk/sites/default/files/MSIS-29.pdf>

Data and Specimen Banking

No specimen collected.

Data Analysis Plan

The data in this small sample will be reported using descriptive statistics such as number and percent. Measures of central tendency such as mean, median and mode will be analyzed for trends or results. A third party, [name], will provide statistical analysis based on psychometric data and objective date with minimally clinically significant changes for these measures. [name] will assess and analyze her own data measures. [name] will assess Hoffman's reflex test and provide the results to [name] and [name]. [name] does not have a role in the study beyond making the Hoffman's reflex test results available for use in this study. All study results will be made available to [name], lead investigator. I will pass these results to [name]. All of the participants 18 HIPAA identifiers will be protected using a numerical system per participant in all transmissions.

Provisions to Monitor the Data to Ensure the Safety of Subjects

[name], upon collection of results the protocol will be updated to when each case study with an individual is complete. I will also review the collected data after each 6-week period of working with the subject.

Withdrawal of Subjects

All participants will participate on an at will basis and will be allowed to discontinue at any time. If a participant is participating and develops an exclusion criterion such as pregnancy they will be withdrawn from the study per the disclosure notice. Forty-eight hours in advance of discharge from home health physical therapy and termination of the study, participants will sign the Notice of Medicare Noncoverage form. If a participant participates in part but not all of the study, data will be collected and stored to be determined in collaboration with statistician at what level their data can be used for *analysis*.

Risks to Subjects

This study carries very low risk to subjects. Possible risks include fatigue from the NeuBie device and exercises used. Subjects with comorbidities that would make participation unsafe will not be included in the study.

Potential Benefits to Subjects

Relaxation of muscle spasm
Decrease in spasticity
Prevention or retardation of disuse atrophy
Increasing local blood circulation
Neuromuscular re-education
Maintaining or increasing range of motion

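### Hoffman's reflex, a planned pre/post outcome for the spasticity endpoint, is the only listed outcome absent from every SAP analysis, and no reason is given

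*SAP*

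**What the plan says.** **Protocol.** Study Endpoints sets the aim: "The primary study endpoint of this pilot study to assess if decrease in spasticity for individuals with MS is possible", during treatment and for any time afterwards. It adds that the listed measures were chosen with that endpoint in mind, and it ranks none of them above the others.

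Procedures Involved gives the timing: "Outcome measures objective and subjective will be collected at the beginning and end of the study". Eight outcomes follow, and Hoffman's reflex is the second. Its tester "performs test only, then gives results to investigators".

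The mail text under Recruitment Methods places the first reflex test at the same visit as EDSS ("then you will be arranged in same office on same day to see" the reflex tester) and describes a return appointment for re-testing after treatment. Funding Source names the reflex test as a funded cost. The Data Analysis Plan says the tester "does not have a role in the study beyond making the Hoffman's reflex test results available for use in this study".

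**SAP.** There are three sets of analyses: a repeated-measures ANOVA for measures taken three times, paired t-tests for measures taken twice, and counts for MAT and MMT. The rule for the second set is "Paired samples t-tests were used to assess for mean change over time for continuous variable measured at 2 timepoints (pre and post". Its table opens with "The data below were collected at 2 timepoints" and has three rows: EDSS, MSIS29 and MSWS12. The SAP does not mention Hoffman's reflex anywhere.

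**The concern.** A measure that was planned, scheduled, funded by name and meant for use in the study has dropped out of the analysis without comment. It also bears on the primary endpoint. The protocol's background cites changes in the H-reflex as effects of earlier spasticity treatments, both for light stroking of the lower limbs and for peroneal nerve stimulation.

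Of the eight outcomes, I read two as direct measures of spasticity: Modified Ashworth and Hoffman's reflex. The others cover disability, walking, strength, mobility and patient-reported impact. With the reflex absent, someone using the SAP to judge spasticity has only the manual ratings. That reader cannot tell whether the planned electrophysiological measure agrees with them, disagrees with them, or exists.

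**Working it through.** No calculation in the plan is in question. The check matches the protocol's outcome list (Procedures Involved) against every SAP analysis.

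| Protocol outcome | Where it appears in the SAP |
|---|---|
| 1. EDSS | Two-timepoint table |
| 2. Hoffman's reflex | Nowhere |
| 3. 12-item MS walking scale | Two-timepoint table (MSWS12) |
| 4. Manual muscle test | Counts (MMT) |
| 5. Modified Ashworth | Counts (MAT, 12 rows), if MAT means Modified Ashworth |
| 6. 25-foot walk | Three-timepoint table |
| 7. Timed Up and Go | Three-timepoint table |
| 8. MSIS-29 | Two-timepoint table |

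The result is 7 of 8 listed outcomes reported and 8 − 7 = 1 unaccounted for, which is 1/8 = 12.5% of the list.

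**Could the reflex be hidden?** The SAP tables show no blacked-out row or gap where a reflex result could have stood.

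**Where would it go?** It was planned at two times, so the two-timepoint set is its natural place if the recorded parameter is continuous. The protocol names no parameter, muscle, side or scale, so that condition is an assumption.

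**Was it done?** EDSS was planned for the same office and day as the first reflex test, and EDSS has pre and post values in the SAP. This shows that EDSS was obtained at both times. It does not show that the reflex test was.

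**Could it have been handled separately?** The Data Analysis Plan has one person assess the reflex test and pass on the results, and another analyse the measures she takes herself. The SAP states that its data were emailed by the physical therapist and describes its goal in terms of function. Separate handling is therefore plausible. Against it, the same protocol section says "All study results will be made available to" the lead investigator, who forwards them, and neither document describes a separate reflex analysis.

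**The case against.** The strongest case on the other side has four parts.

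- **No stated result is wrong.** The SAP draws no conclusion on spasticity, warns that 7 patients is very few, and asks for caution. This stands, and it is why the point is a should-fix and not a must-fix.
- **The endpoint is still covered.** Twelve MAT rows are reported, and the protocol does not place the reflex above the other outcomes. This stands in part. A reader might infer that the primary endpoint was left unanalysed, and the MAT counts show that it was not. What is missing is one planned measure of it.
- **The paired t-test sentence may be correct as written.** If no paired continuous reflex data exist, the sentence covers everything it should. This also stands. The fault is the missing account of a listed outcome, not that sentence.
- **A reflex result would say little.** With at most 7 pairs it would be imprecise, and a pre/post test informs only the after-treatment part of the endpoint. Both are true, but the SAP analyses MSIS-29 and MSWS-12 in the same small sample, so size does not explain why this one outcome is absent.

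A reader might also infer selective reporting, especially since the SAP's two significant findings (right and left hip internal rotation) come from a measure that is not on the protocol's list. The documents do not support that inference. They do not say whether reflex results existed, who held them, or whether anyone saw them before the analyses were chosen.

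**Conclusion.** The point holds as a should-fix. One of eight listed outcomes is unaccounted for, and it was planned as evidence on the primary endpoint. The absence itself can be stated with high confidence. Its cause cannot be settled from the documents: the tests may not have been done, or may have been unusable, handled separately or left out.

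The count of seven reported outcomes assumes that MAT is Modified Ashworth. The statement that direct evidence on spasticity is now MAT alone rests on my classification of the eight measures, since the protocol makes no such division.

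**What to change.** Add Hoffman's reflex to the SAP's pre/post results as a descriptive summary beside the MAT counts:

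- the parameter and side as recorded;
- each participant's pre value, post value and change;
- a mean or median change;
- the number tested at both visits.

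A descriptive summary fits the protocol's own Data Analysis Plan, and no p-value is needed.

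If paired data do not exist or are reported elsewhere, state how many participants were tested at each visit and why the results are absent. Note as well that any statement on spasticity rests on the MAT ratings alone.

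**Cost:** one small table with a line of SAP text if the data exist, or a short disclosure if they do not. No new visits or tests are required.

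### The SAP's only significant findings are on a measure the protocol does not list, at unadjusted p-values; the left side fails Holm adjustment, and the right side's survival depends on which tests are counted

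*SAP*

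**What the plan says.** The SAP's section Summary of Statistically Significant Findings contains a single item: "A linear trend emerged for HIP IR ROM for both the right and the left side". The text before the first table repeats it: "There were 2 significant linear trends reported, Hip IR ROM left and right side". The table rows are "Hip IR ROM R | 6.8 (1.8) | 12.1 (2.1) | 15.3 (2.1) | 0.003" and "Hip IR ROM L | 10.7 (2.3) | 13.4 (1.3) | 17.9 (1.5) | 0.016".

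The Analyses section says that linear and quadratic trends were both assessed for variables measured at three time points. One p-value per variable is printed, and on the quadratic trends the text says only "There were no quadratic trends reported". For the pre/post measures it says "P -values are not significant". MAT (taken here to be the Modified Ashworth test) and MMT are descriptive, without p-values. Neither an alpha nor a multiplicity adjustment is stated. A note near the top warns about the sample of 7 and its heterogeneity, and adds "These results should be considered a pilot and interpreted with caution".

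The protocol (Procedures Involved) lists eight outcomes: EDSS, Hoffman's reflex, MSWS-12, manual muscle test, Modified Ashworth, 25-foot walk, TUG and MSIS-29. Range of movement appears elsewhere in the protocol: in the electrode-mapping step, which compares range with the initial assessment, and under Potential Benefits. Study Endpoints names a decrease in spasticity as the primary endpoint. The Data Analysis Plan starts from descriptive statistics and leaves further analysis to a third party. It names no test, alpha or test family.

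**The concern.** The only claim of an effect backed by a test rests on a measure outside the protocol's outcome list. That measure supplied the two smallest of at least a dozen p-values, which are reported as if each stood alone. Both sides receive the same unqualified label, although p = 0.003 and p = 0.016 stand up very differently once the number of tests is counted.

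The summary also does not say that the measure is unlisted, or how the listed outcomes fared. Someone who reads only the summary would take away a positive result and would not learn that no listed outcome given a p-value showed one. The caution note gives sample size and heterogeneity as reasons for care. Multiplicity and the choice of measure are different reasons, and it mentions neither.

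**Working it through.** **Inputs.** The 12 printed p-values in the SAP tables, sorted: 0.003 (hip IR right), 0.016 (hip IR left), 0.134, 0.189, 0.199, 0.210, 0.277, 0.312, 0.321, 0.370, 0.397, 0.470. Ten come from the three-time-point models (taken as linear trends) and two from paired t-tests. EDSS is marked NA and is not counted. Assumptions: alpha is 0.05, and each of the 10 unprinted quadratic p-values exceeds 0.05, because none was reported.

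**The plan's own figures.** They cannot be reproduced exactly without patient-level data, but they are feasible. With three equally spaced times, the linear contrast is a paired comparison of post with pre. Assume 7 patients, so 6 df.
- Right: p = 0.003 gives t = 4.80. The change is 15.3 − 6.8 = 8.5, so its SE is 8.5/4.80 = 1.77. The implied pre-post correlation is (1.8² + 2.1² − 1.77²)/(2 × 1.8 × 2.1) = 0.60.
- Left: p = 0.016 gives t = 3.32. The change is 17.9 − 10.7 = 7.2, so its SE is 7.2/3.32 = 2.17. The implied correlation is (2.3² + 1.5² − 2.17²)/(2 × 2.3 × 1.5) = 0.41.

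Both correlations are plausible. The summary gives the right-side starting mean as 6.9 and the table gives 6.8; this does not affect what follows.

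**Holm adjustment.** In a family of m tests that contains both sides, the right is m × 0.003 and the left is (m − 1) × 0.016.

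| Family | m | Right | Left |
|---|---|---|---|
| Four hip rotation tests | 4 | 0.012 | 0.048 |
| Eight unlisted ROM and muscle-length tests | 8 | 0.024 | 0.112 |
| All printed p-values | 12 | 0.036 | 0.176 |
| Linear and quadratic trends | 20 | 0.060 | 0.304 |
| All tests assessed | 22 | 0.066 | 0.336 |

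Over the 12, the third smallest gives 10 × 0.134 = 1.34, so every other adjusted value is 1.00.

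**Rounding of the printed p-values.** Right (0.0025 to 0.0035): 0.030 to 0.042 over 12, 0.050 to 0.070 over 20, and 0.055 to 0.077 over 22. Left (0.0155 to 0.0165): 0.171 to 0.182 over 12. The verdicts over 12 and over 22 do not change. Over 20, the lower end just touches the threshold.

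**Dependence on the family.**
- Left: with the right side in the family, it passes with 4 tests (3 × 0.016 = 0.048) and fails with 5 (4 × 0.016 = 0.064). Without the right side, it passes with 3 (0.048) and fails with 4 (0.064). It therefore passes alongside at most two of the other ten printed tests, which is 1 + 10 + 45 = 56 families with the right side and 56 without: 112 of the 2048 that contain it. No passing family has more than 4 tests.
- Right: 16 × 0.003 = 0.048 passes and 17 × 0.003 = 0.051 fails. It passes in every family drawn from the 12 printed tests, but that exercise leaves out the quadratic tests by construction.

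**Listed outcomes.** Four of the eight have a p-value: 25-foot walk 0.370, TUG 0.321, MSIS-29 0.397, MSWS-12 0.277. Mean EDSS is 6.8 at both times. Modified Ashworth and MMT are descriptive. The SAP shows no Hoffman's reflex result.

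**The case against.** The strongest reply is that this is a pilot in 7 patients, with no confirmatory test planned and an explicit call for caution, so formal family-wise control is a matter of preference. That is fair as far as it goes. But if no adjustment is made because the work is exploratory, the result should be labelled exploratory, and the SAP instead calls it significant without qualification.

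Second, nothing is concealed: all 12 p-values are in the tables, the two sides' p-values appear separately, and a section limited to significant findings need not list the others. This stands against any charge of hiding results. It does not answer the point that the summary is silent on the measure's status.

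Third, the family is arbitrary, and Holm, which needs no independence assumption, can be conservative when tests are positively correlated, as two sides of one measure may be. This also stands, and it is why two families should be shown.

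Three stronger readings are tempting, and the documents support none of them:
- That the right side is confirmed because it passes over 12 tests. The SAP says quadratic trends were assessed too, and counting them takes it to 0.066.
- That the right and left hips responded differently. The gains are similar (8.5 and 7.2), and no comparison of sides was made.
- That hip rotation was picked after the results were seen. The SAP is written in the past tense and neither document shows when the measure was chosen. The mapping step presupposes some initial assessment of range, although that does not make it a listed outcome.

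**Conclusion.** The point holds and is minor. The label for the left side is not supported in any family of five or more printed tests (0.176 over 12). The label for the right side is supported over the 12 printed tests (0.036) and not over the 22 assessed (0.066), and neither document gives a reason to prefer one count over the other. The right-side result should therefore be described neither as lost nor as confirmed.

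This rests on an assumed alpha of 0.05, on the absence of any stated adjustment meaning that none was made, and on the unprinted quadratic p-values all exceeding 0.05. That hip internal rotation is absent from the protocol's list, and that none of the four listed outcomes given a p-value reached significance, can be read directly from the documents.

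**What to change.** 1. Label both hip internal rotation results exploratory, drop the unqualified significance wording for both sides, draw no difference between sides, and state that hip ROM and muscle length are not protocol-listed outcomes.
2. Print Holm-adjusted values beside the raw p-values for both families, without naming one as the main family: 12 printed tests, right 0.036 and left 0.176; 22 assessed tests, right 0.066 and left 0.336.
3. Add to the summary that no protocol-listed outcome tested was significant (with the four p-values above), that mean EDSS was unchanged, that MAT and MMT are descriptive only, and that no Hoffman's reflex result is shown.
4. Extend the caution note to cover multiplicity and the unlisted measure.

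The cost is a few sentences and arithmetic on p-values already printed. No new data or reanalysis of patient-level data is needed. The downside is a less favourable headline.

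### Does the erratic right hamstring row in the SAP's table of means show a data error or a wrong number of patients?

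*SAP*

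**What the plan says.** The SAP's goal is to "Evaluate 7 patients with MS on functional scale prior, during, and post participation in a rehab program". Its table for the three-time-point variables gives a mean and standard error before, during and after the programme, plus a P-value. It has no column for n or for unit. The right hamstring row reads "Hamstring length R | 67.5 (4.4) | 52.5 (18.7) | 55.0(15.6) | 0.470".

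Other rows that bear on the question are "Quad Length R | 122.5 (5.9) | 130.8 (1.6) | 130.0 (2.6) | 0.312", "Quad Length L | 121.7 (5.6) | 130.0 (1.3) | 130.8 (2.4) | 0.210", "Hip IR ROM L | 10.7 (2.3) | 13.4 (1.3) | 17.9 (1.5) | 0.016", "Hip ER ROM R | 34.3 (6.3) | 38.6 (5.5) | 38.3 (6.0) | 0.199" and "TUG Test | 27.2 (9.2) | 23.6 (6.9) | 16.5 (0.4) | 0.321". In the categorical table that follows, some rows openly hold fewer than 7 patients, for example "MMT lumbar ext B | 1 | 0 | 4 | 20.0% | 0.0% | 80.0", where 1 + 0 + 4 = 5.

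The protocol (Procedures Involved) lists eight outcome measures. TUG is one of them; hamstring length is not. It plans collection only at the start and the end. The SAP's opening note warns that the sample is very small and mixed, and that the results are pilot findings. The only significant findings it lists are the linear trends in hip internal rotation.

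**The concern.** A standard error that quadruples in the same few patients, on one side only, is what a wrong sign, a switch of measuring convention or a typing error looks like. The left hamstring moves the other way: its mean rises from 64.0 to 74.0 and its standard error falls from 7.8 to 3.7.

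A reader told of 7 patients will also take every mean as an average over 7. On whole-unit readings several rows cannot be that. If a value were wrong, correcting it could shrink or reverse the printed 12.5-unit fall. If patients were missing, the reader would not know which rows were affected.

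**Working it through.** All inputs come from the SAP tables. Assumptions made here, because the documents are silent: the same patients at each time point, and, where stated, whole-unit readings or P taken as the pre-to-post linear contrast. Limits allow for rounding to one decimal.

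**1. Size of the jump.** 18.7/4.4 = 4.25 and 15.6/4.4 = 3.55. The largest ratio in any other row is 2.1/1.8 = 1.17 (right hip internal rotation).

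**2. What the jump implies, with no assumption about unit or scale.**
- The SD of the pre-to-during change is at least (18.65 − 4.45)√n = 28.4 (n=4), 34.8 (n=6), 37.6 (n=7).
- The largest single change is at least √(14.9² + ((n−1)/n)·SD²) = 28.8, 35.1, 37.8.
- The lowest during reading is at most mean − SE = 52.55 − 18.65 = 33.9.
- The lowest baseline reading is at least 67.45 − 4.45(n−1) = 54.1 (n=4), 40.75 (n=7).

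So at least one patient shows a large fall, or at least one reading is wrong.

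**3. Which n the means allow on whole units, for n from 3 to 7.** At n=7, 472/7 = 67.43 and 473/7 = 67.57, so 67.5 cannot occur; 367/7 = 52.43 and 368/7 = 52.57, so 52.5 cannot occur.

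| Row | n that fits all three means |
|---|---|
| Hamstring R | 4 or 6 |
| Quad R | 4 or 6 |
| Quad L | 6 only |
| Hip IR L | 7 only |
| Hip ER R | 7 only |

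For quad L, n=4 would need 487/4 = 121.75 rounded down and 523/4 = 130.75 rounded up in the same row. At n=6 it works: 730/6 = 121.67, 780/6 = 130.0, 785/6 = 130.83. With half-unit readings, n=7 fits every row in this table.

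**4. Can ordinary data give the hamstring row?** Yes.
- n=4, during: 17, 24, 79, 90 gives 52.5 (18.7).
- n=4, pre 57, 64, 72, 77 gives 67.5 (4.4); post, in the same patient order, 73, 9, 62, 76 gives 55.0 (15.6). The paired P is 0.470, as printed.
- n=6, during: −40, 60, 65, 75, 75, 80 gives 52.5 (18.7); post: −20, 50, 70, 75, 75, 80 gives 55.0 (15.6). These sets need one negative reading.

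The printed figures cannot separate these explanations.

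**5. How much the row says.** If P=0.470 is the linear contrast, t = 0.825 (n=4) or 0.781 (n=6). The SE of the change is 12.5/t = 15.2 or 16.0, and the 95% interval is −12.5 ± 3.182 × 15.2 = −61 to +36, or −12.5 ± 2.571 × 16.0 = −54 to +29.

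**6. TUG.** If P=0.321 is the linear contrast, take the smallest difference, 10.6, and the largest possible SE of change, 9.2 + 0.4 + 0.1 = 9.7. The maximum P is then 0.354 (n=4), 0.336 (n=5), 0.324 (n=6) and 0.316 (n=7). So n=7 is excluded by only 0.005. At the figures as printed (10.7 and 9.6) the maximum at n=6 is also 0.316, so n=6 survives only at the rounding limits.

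**The case for a change.** The best case for acting is that the anomaly in steps 1 and 2 needs no assumption about unit or scale, and any range check would flag it. Denominators below 7 are a fact in the categorical table, where the counts reveal them; in the table of means they are hidden. The SAP's general caution about 7 patients does not tell a reader that some rows may rest on fewer, or that a value may be mistyped. TUG, which is a protocol outcome, hints the same way. The cost is a look at records for at most 7 people and two extra columns.

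Most of that stands as a description. The row deserves a query, and n and unit would make the table easier to read. What does not stand is the step from there to a fault in the plan. The exclusion of 7 depends on a measuring resolution the documents never give. Narrowing the row to n=4 would also need a 0–90 scale, which they do not give either. The TUG margin is very thin and rests on how P was formed. Missing timed walks would also be unsurprising: the protocol's Inclusion Criteria admit people unable to walk more than 150 feet at a time, and mean EDSS is 6.8. The figure of 7 is the number of patients evaluated; the SAP never states it as the n of each row.

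**Conclusion.** The row is unusual, and the suspicion is reasonable, but no error is demonstrated and no result is shown to change. The printed fall of 12.5 units has an interval of roughly −61 to +36 (n=4) or −54 to +29 (n=6), if P is the linear contrast. It is non-significant, concerns a measure outside the protocol's list, and supports no conclusion. The hip internal rotation findings do not depend on it: on whole units the left side fits n=7, and so does the right side using the 6.9 printed in the SAP's summary (48/7 = 6.86; the table prints 6.8).

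What remains is a data query that anyone holding the source sheets would raise and close, and two missing descriptors, n and unit, that an analyst supplies from the output when the table is reported. Neither alters the design, the analysis method or what may be concluded. The inferences about n rest on whole-unit readings; with half units the means in all the rows tabulated above are compatible with 7.
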